8.2 Handling of Missing Data and Intercurrent Events

Missing data could occur due to various reasons, including missing visits/assessments, early withdrawal from the study, or missing due to COVID-19 infection or logistic restriction.

The COVID-19 pandemic is interfering with the conduct of many ongoing trials, with potential impacts on treatment duration and the collection, analysis, and the interpretation of clinical trial data. Some protocol-specified visits in the clinical trials may be impacted due to COVID-19 infection or logistical restrictions during the pandemic. For example, some scheduled visits may be missed due to self-quarantine or local government restrictions on travel; some visits may also be delayed or canceled due to healthcare resource constraints during the pandemic. Impacted visits due to COVID-19 will be recorded in the database. The probability of having missed visits and missing data due to COVID-19 infection or logistical restrictions related to the COVID-19 pandemic can be

reasonably assumed to be unrelated to the unobserved values. Therefore, for the purpose of statistical analysis, it is reasonable to assume that these missing data are missing at random (MAR) and the statistical models that require MAR assumption are appropriate. The intent is to provide reliable estimates of the treatment effects targeted in the protocol under the scenario without the impact of COVID-19 pandemic. Sensitivity analyses will be performed to assess the impact of missing data and the robustness of the conclusion. Number of subjects with missing values due to COVID-19 will be presented.

Intercurrent events includes initiation of rescue medication and initiation of concomitant medications for PsA use that could meaningfully impact efficacy assessment. Missing data and intercurrent events will be handled using the following methods for the efficacy analysis.

Non-Responder Imputation incorporating Multiple Imputation (MI) to handle missing data due to COVID-19 (NRI-C)

The NRI-C data handling will be used for the primary estimand (refer to Section 8.3.1) for the binary endpoints. It will handle data for binary variables as follows.

- a. Missing data due to COVID-19 infection or logistical restriction related to COVID-19 pandemic will be handled by Multiple Imputation.
- b. Subject who does not have evaluation during a specific visit window due to reasons other than COVID-19 infection or logistical restriction related to COVID-19 pandemic will be handled by NRI for that visit. NRI will consider a subject with missing evaluation as a non-responder with the exception for composite binary endpoints including ACR20, ACR50, ACR70, MDA and modified PsARC for which the missing components will be imputed with last observation carry forward to derive composite score before imputing missing evaluations as a non-responder.
- c. Subjects will be considered as non-responders after initiation of rescue medication or initiation of concomitant medications for PsA that could

meaningfully impact efficacy assessment; these medications will be identified prior to database lock and unblinding.

For composite binary endpoints including ACR20, ACR50, ACR70, MDA and modified PsARC, the missing binary values due to COVID-19 infection or logistical restriction will be imputed via MI with the logistic regression option as outlined in [Appendix F](#). For other binary endpoints which are dichotomized from a continuous scale, the MI will be applied to the original continuous scale and the dichotomized endpoint will be derived from the imputed value for missing due to COVID-19 infection or logistical restriction.

Mixed-Effect Model Repeated Measures (MMRM)

The repeated measures analysis will be conducted using a mixed model including observed measurements at all visits. For the MMRM analysis, data collected after initiation of rescue medication or initiation of concomitant medications for PsA use that could meaningfully impact efficacy assessment will be excluded. The mixed model includes the categorical fixed effects of treatment, visit and treatment-by-visit interaction, stratification factors, and the continuous fixed covariate of baseline measurement. An unstructured variance covariance matrix will be used. Parameter estimation is based on the assumption of data being missing at random and using the method of restricted maximum likelihood (REML). The MMRM approach is appropriate in handling missing data due to COVID-19 infection or logistical restriction given the validity of the missing at random assumption. MMRM will be used for the primary estimand of continuous variables (refer to Section 8.4.1).

As Observed (AO)

The AO analysis will not impute values for missing evaluations, and thus a subject who does not have an evaluation on a scheduled visit will be excluded from the AO analysis for that visit. Regardless of premature discontinuation of study drug, initiation of concomitant medications for PsA use that could meaningfully impact efficacy assessment,

or initiation of rescue medication, all observed data will be used in the analysis. The AO analysis will be used to facilitate the supplementary analysis.

AO with Imputation

The AO with imputation will use all observed data regardless of premature discontinuation of study drug, initiation of concomitant medications for PsA use that could meaningfully impact efficacy assessment, or initiation of rescue medication and will impute missing as non-responders. It will be used for the supplementary analysis for binary variables.

Multiple Imputation (MI)

As a sensitivity analysis, MI will be utilized for both hypothetical and treatment policy estimand ([Appendix D](#)). MI analysis will be performed based on AO data. The MI analysis will impute missing data multiple times under appropriate random variation and thus generate multiple imputed "pseudo-complete" datasets. SAS PROC MI will be used to generate 30 datasets using the fully conditional specification (FCS) method. Specifically, treatment group is included in the FCS imputation model to enable stratified sampling. Additionally, the imputation model includes demographics variables, baseline disease characteristics, stratification factors, as well as longitudinal response observed at any other visits. Analysis using CMH for binary endpoints and analysis of covariance (ANCOVA) for continuous endpoints will be performed on each of the multiple imputed datasets. Subsequently SAS PROC MIANALYZE will then be used to aggregate the results for the final statistical inference using Rubin's method.¹

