7.3 Statistical Analyses for Efficacy

Imputation Methods

Non-Responder Imputation incorporating multiple imputation to handle missing data due to COVID-19 (NRI-C): Subjects with a missed scheduled assessment visit due to reasons other than the COVID-19 pandemic will be handled by non-responder imputation. In addition, subjects will be considered as non-responders after the initiation of concomitant medications for PsA that could meaningfully impact efficacy assessment or initiation of rescue therapy. Missing data due to a COVID-19 infection or logistical restrictions related to the COVID-19 pandemic will be handled through multiple imputation.

As Observed (AO): The AO analysis will not impute values for missing evaluations; therefore, a subject who does not have an evaluation on a scheduled visit will be excluded from the AO analysis for that visit. Regardless of premature discontinuation of study drug, initiation of concomitant medications for PsA that could meaningfully impact efficacy assessments, or initiation of rescue therapy, all observed data will be used in the AO analysis.

Statistical Analyses for Efficacy

The comparisons between the risankizumab and placebo treatment groups for the primary efficacy endpoint (ACR20 at Week 24) will be performed using the Cochran-Mantel-Haenszel (CMH) test stratified by stratification factors.

For continuous efficacy endpoints, the treatment comparison will be conducted using a Mixed-Effect Model Repeated Measures (MMRM) method as primary inference purpose.

The MMRM analysis will be conducted using mixed-effect model with observed measurements at all visits prior to initiation of any concomitant medications for PsA that could meaningfully impact efficacy assessments or rescue medications. The mixed model includes the categorical fixed effects of treatment, visit and treatment-by-visit interaction, main stratification factors, and the continuous fixed covariate of baseline measurement. An unstructured variance covariance matrix will be used. The parameter estimations are based on the assumption of data being missing at random and using the method of restricted maximum likelihood (REML).

Categorical efficacy variables will be analyzed using the CMH test controlling for stratification variables. NRI-C imputation will be used for missing data imputation.

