2.3 Treatment Assignment and Blinding

Subjects will be randomized to risankizumab 150 mg or placebo in a 1:1 ratio.

Randomization will be stratified by current use of csDMARD (0 vs ≥ 1), number of prior biologic therapies (0 vs ≥ 1), and extent of psoriasis ($\geq 3\%$ BSA or $< 3\%$ BSA).

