2.4 Sample Size Determination

Approximately 420 subjects will be randomized to risankizumab 150 mg or placebo in a ratio of 1:1 (210 subject/treatment group). A sample size of 210 in each group will have approximately 90% power to detect a difference in HAQ-DI mean change from baseline of 0.24 assuming that the common standard deviation is 0.72 using a two group t-test with a 0.05 two-sided significance level and accounting for a 10% dropout rate. This sample size also ensures that analyses will have at least a 90% power to detect a 20% treatment difference, with the placebo response rate seen in the previous Phase 2b study of 35.7%, in ACR20 at Week 24 using a two-sided test at a 0.05 significance level and accounting for a 10% dropout rate.

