8.0 Efficacy Analyses

8.1 General Considerations

All efficacy analyses will be conducted in the FAS Population. In addition, Per-protocol analysis for primary endpoint will be performed. All tests will be 2-sided at an alpha level of 0.05.

The Primary Analysis will be conducted after all ongoing subjects have completed Week 24 and the Week-24 Database Lock has occurred. Efficacy and safety analyses will be performed for Period 1 and long-term efficacy and safety will be summarized through the data cutoff date. An additional interim database lock will be conducted to provide further efficacy and safety exposure for integrated summaries of efficacy and safety supporting the initial regulatory submission; no study-specific analysis will be performed based on this database lock.

Unless otherwise specified, categorical variables will be analyzed using Cochran-Mantel-Haenszel (CMH) test, adjusting for the stratification factors. Continuous variables will be analyzed using Mixed-Effect Model Repeat Measurement (MMRM) method.

Unless otherwise specified, any subject who is randomized based on a wrong stratum will be analyzed according to the actual stratum the subject belongs to.

"Baseline" refers to the last non-missing observation before the first administration of study drug or before randomization if no study drug is given.

Efficacy analysis for Period 1

The efficacy analysis for Period 1 will be performed after all ongoing subjects have completed Period 1 and an interim database lock has occurred. This is the only and final efficacy analysis in Period 1.

Long-term efficacy analysis

Long-term efficacy will be summarized based on data in Period 1 and Period 2 up to data cutoff date for the Week-24 Database Lock. After the initial regulatory submission, additional interim analyses will be performed as deemed appropriate, for example, to address requests from regulatory agencies. The final analysis will be performed after all ongoing subjects complete the study.

The long-term efficacy analysis will be performed on As Observed data (defined in Section 8.2) by randomized treatment group sequence as described below:

1. Placebo → risankizumab 150 mg
2. risankizumab 150 mg → risankizumab 150 mg

There will be no statistical testing for long-term efficacy analysis; only descriptive statistics and 95% confidence intervals will be provided.

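### The primary MMRM for HAQ-DI, SF-36 PCS and FACIT-Fatigue fits one baseline slope for all visits; pre-specifying a baseline-by-visit term is a cheap safeguard with a small, conditional gain at Week 24

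*SAP*

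**What the plan says.** The model in SAP 8.2 is: "The mixed model includes the categorical fixed effects of treatment, visit and treatment-by-visit interaction, stratification factors, and the continuous fixed covariate of baseline measurement". Covariance is unstructured, estimation is by REML, and missing data are taken as missing at random. Protocol 7.3 gives the same fixed effects, ending in "main stratification factors, and the continuous fixed covariate of baseline measurement". Neither document lists a baseline-by-visit interaction. Both leave out measurements taken after rescue or after other PsA medication that could affect efficacy.

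SAP 8.4.1 makes this the primary analysis of the continuous secondary endpoints. Three of these are ranked in SAP 3.2: HAQ-DI (first), SF-36 PCS (fifth) and FACIT-Fatigue (sixth), each at Week 24. Under SAP 12.0, HAQ-DI is tested directly after ACR20 in a fixed sequence.

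The visit lists in Operations Manual 2.1 give HAQ-DI at Weeks 4, 8, 12, 16 and 24 in Period 1, and SF-36 and FACIT-Fatigue at Weeks 12 and 24. Rescue is assessed at Week 16 (Protocol 5.4).

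**The concern.** Under the model as written, the relation of change to baseline is the same at every visit. If that relation shifts during follow-up, the fitted slope is a compromise across visits and is not the best adjustment at Week 24, the only visit tested. Two consequences are possible. The residual variance at Week 24 may be larger than it needs to be. And where Week 24 values are missing, the model predicts them from a mean structure that does not quite fit, which can move the treatment difference if missingness depends on baseline and differs between arms. Excluding post-rescue data makes Week 24 the Period 1 visit most exposed to this. An unstructured covariance does not help, because the restriction is in the fixed effects.

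Other parts of the SAP do not share the restriction. The sample code in Appendix F regresses ACR20 at each visit separately on the baseline covariates. The HAQ-DI tipping-point imputation uses the same variables. The ANCOVA in SAP 8.4.2, fitted at Week 24, has its own Week 24 slope.

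**Working it through.** **Inputs from the documents.** Testing: "All tests will be 2-sided at an alpha level of 0.05" (SAP 8.1). Allocation: "Subjects will be randomized to risankizumab 150 mg or placebo in a 1:1 ratio" (SAP 2.3). Planning (SAP 2.4): 210 per arm, about 90% power, 10% dropout, and the HAQ-DI effect and SD given as "mean change from baseline of 0.24 assuming that the common standard deviation is 0.72 using a two group t-test".

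**Step 1, reproduce the plan's power.** Evaluable per arm: 210 × 0.9 = 189. SE = 0.72 × √(2/189) = 0.0741. Power = Φ(0.24/0.0741 − 1.96) = Φ(1.28) = 0.900, which agrees with the SAP. With all 210 per arm, SE = 0.0703 and power = 0.927; Protocol 7.3 does not mention dropout in its HAQ-DI sentence.

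**Step 2, closed form for complete data.** Let β be the vector of baseline slopes by visit, S the residual covariance between visits, s24 the residual SD at Week 24 and σB the baseline SD. The single fitted slope converges to b = (1′S⁻¹β)/(1′S⁻¹1). The Week 24 SE ratio, one slope over interaction, is √(1 + (β24 − b)²σB²/s24²).

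**Assumptions, none of them in the documents.** Baseline SD 0.5, 0.65 or 0.8. Correlation between visits 0.5, 0.7 or 0.85, AR(1) or exchangeable. Slope of change on baseline −0.1 at Week 4, moving in equal steps per visit by a total drift of 0 to 0.3. Residual SD rising linearly over the five visits from 75% to 100% of its Week 24 value. SD of change at Week 24 equal to 0.72.

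**Step 3, one case.** Drift 0.3, σB = 0.65, AR(1) with 0.7. β24 = −0.40 and b = −0.2016. s24² = 0.72² − (0.40 × 0.65)² = 0.4508. Ratio = √(1 + 0.1984² × 0.4225/0.4508) = 1.018, so the SE falls by 1.8%.

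**Step 4, whole grid for HAQ-DI.** Power takes the planning SE as the one-slope SE and divides it by the median ratio.

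| Drift | SE reduction, median (range) | Power at median |
|---|---|---|
| 0 | 0% | 0.900 |
| 0.1 | 0.2% (0.1 to 1.2%) | 0.901 |
| 0.2 | 1.0% (0.4 to 4.7%) | 0.906 |
| 0.3 | 2.5% (0.9 to 10.6%) | 0.913 |

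The largest reduction (10.6%, power 0.952) needs drift 0.3, baseline SD 0.8 and exchangeable correlation 0.85 together. The medians describe the grid, not a probability.

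For the two-visit endpoints (slope −0.2 at Week 12, Week 12 residual SD 95% of Week 24, baseline SD equal to the SD of change), the reductions are 0% at drift 0, 0.2% at 0.1 and 1.8 to 2.6% at 0.3.

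**Step 5, simulation with missing data.** 210 per arm. Mean Week 24 SE, one slope / interaction, from three separate sets of simulations:

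| Missing at Week 24 (two arms) | Drift 0 | 0.1 | 0.2 | 0.3 |
|---|---|---|---|---|
| Set 1: none | 0.0699 / 0.0700 | 0.0694 / 0.0693 | – | 0.0667 / 0.0656 |
| Set 1: 10% at random | 0.0730 / 0.0731 | 0.0718 / 0.0717 | – | 0.0696 / 0.0683 |
| Set 1: rescue-type, 32% / 24% | 0.0779 / 0.0780 | 0.0771 / 0.0772 | – | 0.0738 / 0.0731 |
| Set 2: rescue-type, 27% / 21% | 0.0690 / 0.0690 | 0.0693 / 0.0692 | 0.0700 / 0.0693 | 0.0709 / 0.0694 |
| Set 3: rescue-type, 27% / 24% | 0.0703 / 0.0704 | 0.0707 / 0.0706 | 0.0708 / 0.0700 | 0.0726 / 0.0708 |

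At drift 0.3 the gain runs from 0.9% (0.0738 to 0.0731) to 2.5% (0.0726 to 0.0708). With equal slopes the interaction costs about 0.1 to 0.3% of SE; the pairs shown are at the low end. In set 1 it was the wider model in 75 to 80% of equal-slope trials.

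**Step 6, bias when loss depends on baseline and arm.** True difference −0.240.
- In 150 simulated trials at drift 0.3, the one-slope model averaged −0.248 and the interaction model −0.239.
- In large samples at drift 0.3 (Monte Carlo error about 0.002), two loss patterns gave −0.233 and −0.243 with one slope, against −0.241 and −0.237 with the interaction.
- In a third check, the two models differed by 0.004 to 0.013 at drifts 0.1 to 0.3.
- In the large-sample check the models agreed at drift 0.

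The shift can go in either direction. At most it is 0.013/0.24, about 5% of the planned effect.

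**The case against.** The strongest reply is that nothing is broken. The model is fully specified, agrees between the two documents, and is one of two valid choices. That stands: randomization balances baseline, so with complete data the Week 24 difference is unbiased whatever slope is fitted.

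The second reply is that the premise is not in the documents. They report no slope by visit and no correlation with baseline, so they cannot show that slopes differ. This also stands, and it is why the gain is given only as a range that includes zero and a slight loss.

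The third is that SAP 8.4.2 already adds a Week 24 ANCOVA and, for HAQ-DI, multiple imputation with a tipping-point analysis. That is partial cover: those analyses target the treatment-policy estimand on as-observed data and do not check the slope assumption in the hypothetical-estimand model.

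A reader might infer that the extra term is free precision, that it can be converted into a number of subjects saved, or that it secures the testing sequence because HAQ-DI comes early in it. The documents support none of these. There are extra parameters, and the SE is slightly wider if slopes are equal. A conversion into subjects needs slopes that nobody has stated. It would also go wrong if 0.72 were used as the SD of the Week 24 score: Protocol 7.3 and SAP 2.4 give it as the SD for change. As for the sequence, a little over one point of power at the median for the largest assumed drift is not protection. In the 150-trial check in Step 6, power was 0.873 with one slope and 0.853 with the interaction, because the one-slope estimate had moved away from zero.

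**Conclusion.** The point holds as a modest improvement, not as a correction of an error. The primary MMRM assumes equal baseline slopes at all visits, and nothing in the documents supports or contradicts that assumption. Dropping it costs about 0.1 to 0.3% of the Week 24 SE if slopes are equal. If the slope drifts by 0.1 to 0.3 between Week 4 and Week 24, the SE is typically 0 to 3% smaller, and HAQ-DI power moves from 0.900 to between 0.901 and 0.913 at the median gains. The better reason to act is robustness: with post-rescue data excluded and missingness related to baseline and arm, the one-slope estimate differed from the interaction estimate by roughly 0.004 to 0.013 HAQ-DI units. All of these sizes rest on assumed slopes, correlations, baseline SDs and missingness patterns, and the bias figures come from a few illustrative scenarios.

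**What to change.** Before Week 24 unblinding, add a baseline-by-visit interaction to the MMRM in SAP 8.2 for all continuous endpoints, and align Protocol 7.3 at its next amendment. If the data have already been unblinded, leave the primary model as it is and report the interaction model as a sensitivity analysis.

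The cost is one slope per additional visit: 5 − 1 = 4 parameters for HAQ-DI and 2 − 1 = 1 each for SF-36 PCS and FACIT-Fatigue, against about 420 subjects. The activity table in Protocol Appendix D, as extracted, ticks HAQ-DI in Period 1 only at Baseline, Week 12 and Week 24. That may be a fault of the extraction; if the table is right, the HAQ-DI cost is also one parameter. No change to data collection, sample size or testing order is needed.

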8.3 Primary Efficacy Endpoint and Analyses

8.3.1 Primary Efficacy Endpoint

The primary efficacy endpoint is ACR20 response at Week 24. The attributes of primary estimand based on composite estimand framework are outlined in [Appendix D](#).

8.3.2 Handling of Missing Data and Intercurrent Event for the Primary Efficacy Endpoint

For the primary estimand, NRI-C as defined in Section 8.2 will be used.

Subjects who initiated concomitant medications for PsA that could meaningfully impact efficacy assessment or were rescued prior to Week 24 or missed ACR20 response at Week 24 will be treated as non-responders. The number and percentage of non-responders for ACR20 will be summarized into one of the five categories for which the episode occurs first:

1. Subjects rescued before Week 24
2. Subjects who initiated concomitant medications for PsA that could meaningfully impact efficacy assessment by Week 24
3. Subjects with ACR20 measurements observed at Week 24 but did not meet ACR20 response criteria
4. Subjects with missing Week 24 ACR20 measurements due to reasons other than COVID-19 infection or logistical restriction related to COVID-19 pandemic
5. Subjects with missing Week 24 ACR20 measurements due to COVID-19 infection or logistical restriction related to COVID-19 pandemic

8.3.3 Primary Efficacy Analysis

Analysis of the primary endpoint will be conducted on the FAS based on randomized treatment groups (risankizumab 150 mg versus placebo) using NRI-C for missing data handling. Point estimate and 95% CI using normal approximation will be provided for the response rate for each randomized treatment group. Comparison of the primary endpoint between the risankizumab and placebo groups will be made using the CMH adjusting for stratification factors. Point estimate, 95% CI and nominal p-value for the treatment difference will be presented. Refer to [Appendix E](#) for the details of NRI-C procedure and respective statistical inference.

A sensitivity analysis will be conducted on the Per Protocol Analysis Set using the CMH model and NRI-C missing data handling.

